## Laboratory Specimens

There are no laboratory specimens collected for this study.

## Sample Size Justification

Attrition rates from the ASD pilot study conducted at University of Minnesota were > 30%. This high dropout rate can be ascribed to design issues, in that: (1) the sample recruited for the pilot consisted of adolescents who were not intrinsically interested in long-term treatment options for ASD, unlike the current target (adolescents already seeking PEERS); and (2) study coordinators had not been formally trained on how to keep participants engaged in a remote cognitive training intervention. By recruiting adolescents already seeking PEERS and by rigorously training our staff, we expect retention rate for this project to be in line with those of 1) cognitive interventions delivered to adolescents with ASD; 2) PEERS groups. We project a 15% non-completion rate estimate for this study. We will recruit 56 participants to obtain 48 study completers. As the primary aim of this study is to gather information about the feasibility, acceptability and usability of this approach, the sample size of N=56 is set primarily for practical reasons and not driven by hypothesis testing. This size will, however, provide data to power a subsequent pivotal efficacy trial in Phase II, and will provide the field validation data required to submit CICADAS to the FDA as a medical device for such a trial

under the 510k de novo process. We are confident that we will meet our recruitment goals with these resources in place.

Of interest to the design of our proposed trial, despite randomization to the auditory or visual training conditions, 73.2% of participants who were assigned to the Visual condition at BL completed the training whereas only 38.5% of participants who were assigned the Auditory Condition completed the program. This highlights the importance of personalized intervention programs that take individual differences (e.g., auditory sensitivity) into consideration. In fact, several participants who chose to discontinue attributed their decision to an aversion to the auditory stimuli used in the computer programs. Baseline SCAN Competing Words Test scores were significantly related to whether individuals randomized to the Auditory or Visual NB-SCT Modules completed their training [ $F(2,23) = 6.331, p = .006$ ]. In other words, participants randomized to the Auditory NB-SCT who did not complete their program had significantly more auditory processing difficulties than those who completed the program.

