### ***Intervention Embedded Assessments***

All participants, regardless of treatment group, will complete the ten sensory processing assessments before and after the first intervention period.

**The primary outcome** measures, including digital assessment completion rate, NB-SCT program adherence, usability ratings, reported adverse effects, and overall program completion rate will be used to assess feasibility, acceptability and usability of CICADAS app.

**Secondary outcomes** measures include baseline, mid-intervention, and post-intervention assessments as well as the weekly number of initiated or reciprocated social gatherings related to or in addition to PEERS assigned social activities.

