- *Extra Time:* Under special circumstances, PEERS session(s) may be paused for 1 or more weeks. This may occur if the PEERS Clinician is unable to conduct the session and no alternate PEERS Clinician is available to conduct the session. In such cases, the intervention will be extended by the number of weeks it has been placed on hold. Participants will resume the PEERS sessions such that all 16 sessions intended for the intervention are delivered to participants.
- *Cessation of Program Use While Continuing Participation in the Study:* In some cases, a participant may wish to stop or minimize use of the program, while remaining in the study. Potential reasons for this decision might include changes in school or work circumstances, changes in residence, health issues, family/personal issues, or a lack of interest in program activities. While the participant will be encouraged to meet their weekly goals, in such cases, after discussion with the site study coordinator, the participant will be permitted to cease using the program and undergo the mid-intervention assessment (V3) or post-intervention assessment (*End of Study*, V4) visit, given they have met the minimum number of sessions required to complete this assessment.
- *Emergency:* All participants will be told how to contact the appropriate site study personnel in the case of an emergency.

Several of these options in aggregate are likely to lead to variation within a group and between groups with regard to the total number of sessions completed, and may cause an imbalance between the number of sessions completed within and between groups. Although this is not ideal, we believe that this is the correct approach given that such flexibility will allow more participants to join the study (compared to no program use flexibility), and reduce attrition. In addition, this approach has the value of more closely mimicking real-world use of the program, increasing the prospective validity of the study. We will continuously monitor the distribution of completed sessions and will consider modifications to the protocol (see *Modifications to the Protocol*) if it appears that this flexibility may be associated with meaningful differences. The data analysis plan is generally robust to variations in the number of sessions completed (see *Data Analysis*).

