Each study participant will be remotely supervised by a site study coordinator. Participants may be contacted once per week by a member of the study team to discuss participant engagement with the CICADAS or Active Control apps or intervention activities, and contact may adjusted depending on each participant's needs. Based on our previous experiences with in-residence trials, we have developed protocols and training that will allow the site study coordinator and PEERS clinicians to establish rapport with participants, identify and tend to any barriers to program use or compliance (such as establishing reminders to complete assessments or reducing distracters in the environment), and to provide feedback and support

around performance. The site study coordinator and PEERS clinician will also be specifically trained to deal with specific issues that might arise with individuals with ASD.

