## Foreseeable Risks, Risk Management & Emergency Response

Participation in the study presents minimal risk. The probability and magnitude of harm or discomfort anticipated in this research study are not greater than those ordinarily encountered in daily life or during the performance of routine physical or psychological examinations or tests.

Serious adverse effects from prior studies of the treatments under study have not been reported. The protocol details potential risks related to study participation and includes assessments of increased risk of suicidality.

The following foreseeable risks will be discussed with potential participants during the enrollment visit, as will the following measures taken to minimize such risks:

- *Diagnostic interview and self-report measures.* Participants may feel uncomfortable or embarrassed due to sensitive questioning about their psychiatric condition and medical history during the diagnostic interview or on self-report measures. Participants will be reminded during each appointment that their participation in the study is voluntary and that as such, they are not required to complete any assessments and may skip individual questions or assessments entirely.
- *Discomfort During Assessments:* Assessments may be fatiguing for some individuals, particularly for those with persistent cognitive symptoms. To minimize this potential discomfort, breaks are encouraged and scheduled within the session. In the event that a participant appears to be under undue strain, test sessions are discontinued.
- *Lack of Assessment Feedback:* Participation in this study does not include feedback to participants on their individual assessment results. Though participants are informed of this policy during consent, some participants may find the lack of feedback to be frustrating.
- *Discomfort During Intervention/Program Use:* The following risks may be reasonably anticipated as the result of intervention and/or program use: fatigue, mood complaint, headache, tremor, eye strain, neck/shoulder discomfort, leg/hip discomfort, arm/wrist discomfort, back discomfort, headache and sleep difficulty. To minimize the fatigue participants are encouraged to sit ergonomically correctly while completing study activities on their device. The program is also designed to be entertaining and enjoyable. In addition, assessment and self-report sessions may be paused at any time and participants are encouraged to take breaks.

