- *Other Risks:* Although it has not been previously documented, it is possible that the use of the investigational program or participation in the study activities may cause symptoms to worsen. There may also be risks related to the use of the program that are unknown at this time.

- *Loss of Privacy:* The most significant risk to the participants are those that would follow a breach of confidentiality and the disclosure of clinical information. Participation in any research study, including this one, may involve a loss of privacy, and absolute confidentiality cannot be guaranteed. Procedures designed to maintain data confidentiality include (1) formal protocol training sessions for all study team members emphasizing the importance of confidentiality, (2) adherence to specific procedures developed to protect participants' confidentiality, and (3) formal mechanisms limiting access to information that can link data to individual participants. One reason for breaking confidentiality is that the study personnel are required by law to report cases of physical or sexual abuse to local law authorities; and another is that despite all procedures, an error may occur. To mitigate this risk, data forms that include identifying information, with the exception of dates assessments are completed, date of birth, and dates associated with other data collected, and personally identifying information volunteered by participants in the Zoom chat forum, will be kept in locked cabinets or secure servers at the site, and accessible only to authorized study personnel. Only the unique ID number, assigned by the study coordinator, will represent participants during participation in the study. In the Zoom platform, participants will have the choice to self-identify with their first name or an alias. To facilitate tracking, a password-protected computer file will be maintained containing the identity of participants, their ID numbers, and contact information. This file, however, will contain no clinical data. Electronic data will be password protected and stored on a secure network. All data keys will be stored separately and securely. Only study personnel will have access to the study data. No participant names will be used in study reports or publications.

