### Withdrawal from the Protocol

Study participants may withdraw from the study at any time, for any reason, or for no stated reason. We anticipate that a common reason for study withdrawal will be the time required to complete the intervention. For participants seeking to withdraw for that reason, we will offer the alternative of discontinuing the intervention and scheduling and completing the post-intervention assessment (*End of Study, V4*) visit, given they have met the minimum sessions required to complete the assessment visits. The data analysis plan is structured so that their data will be valuable even if they do not complete the intended number of sessions. Participants who still wish to withdraw following that option will withdraw. Other than time required to use the program, we do not anticipate any common reasons for withdrawal that we will plan for in advance.

In rare cases, a Principle Investigator may decide to prematurely discontinue a participant's involvement in the study for any of the following reasons:

- a) Safety,
- b) Participant non-compliance,
- c) A change in circumstance that would prevent completion of protocol-required assessments,
- d) Participant relocation to an area that, due to great distance, would prohibit a participant from receiving follow-up at the study site,
- e) Participant displays inappropriate behavior toward study staff members or other participants,
- f) Participant is hospitalized for psychiatric reasons;
- g) Loss of funding, or;
- h) A clinical determination, by the Principal Investigator, that continuation in the study is not in the participant's best interests.

Across all reasons for withdrawal, we will ensure an orderly end to the participant's involvement in the study by arranging for the site study coordinator or PEERS clinician to recover the digital device (if it has been issued to the participant), conducting an informational interview with the participant to understand the reasons for study withdrawal and identify any issues with study conduct or adverse events that are relevant, and arrange study compensation for sessions that the participant completed.

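### Aversion to the sounds made pilot participants stop, yet the plan neither names it nor reports stops by reason, and the side-effect outcome leaves out Arm A participants who leave before PEERS

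*Protocol*

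**What the plan says.** **The pilot.** The Protocol (Sample Size Justification) states that "several participants who chose to discontinue attributed their decision to an aversion to the auditory stimuli used in the computer programs". It gives completion of 38.5% in the auditory condition and 73.2% in the visual condition, without denominators, and offers personalisation as the response.

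**Risks and withdrawal.** In Foreseeable Risks, the list opening "The following risks may be reasonably anticipated as the result of intervention and/or program use" covers tiredness, mood, headache, tremor, eye strain, musculoskeletal discomfort and sleep, and nothing auditory or sensory. A general line adds that "it is possible that the use of the investigational program or participation in the study activities may cause symptoms to worsen". Withdrawal from the Protocol says: "Other than time required to use the program, we do not anticipate any common reasons for withdrawal that we will plan for in advance".

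**Routes for learning the reason.**
- Staff are trained to "identify and tend to any barriers to program use or compliance" (Description of Protocol Devices).
- Stopping the app while staying in the study follows a conversation: "after discussion with the site study coordinator, the participant will be permitted to cease using the program" (same section).
- Withdrawal includes "conducting an informational interview with the participant to understand the reasons for study withdrawal and identify any issues with study conduct or adverse events" (Withdrawal from the Protocol).
- Staff ask about deterioration at each contact (Reporting of Serious Adverse Effects).
- Appendix I schedules an Adverse Effects form at V1, V3 and V4, and Unanticipated Adverse Effects and Study Exit forms as needed.
- First app use, at V2, is proctored (Study Procedures).

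**The analysis.** SAP, Primary Outcome - Feasibility, item 4 is reported side effects, with zero adverse events expected from program use. It is analysed in the ITT-CU (CICADAS-Users) population. SAP, Design and Analysis Populations defines ITT-CU as ITT members given both CICADAS and PEERS, and makes one PEERS session a condition of ITT membership. The opening summary of the same section describes the fourth population more loosely, as those allocated to have CICADAS.

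**The concern.** The sponsor's own pilot in this population identified a reason for stopping that comes from the product itself. The two causes that the Protocol gives for the pilot's attrition of over 30% are low interest in treatment and untrained coordinators; sound aversion is not one of them. The withdrawal section then plans only for time burden.

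Personalisation may solve the problem, but that is a premise for this trial to test. The table under Treatment Interventions still contains sound-based content, and no section says that such content is withheld from sound-averse participants.

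Items 2 and 5 would fall if people stopped, without showing why. Item 4 is where poor tolerability should appear, but its population can omit the people concerned. Arm A is half of those given CICADAS, and it has no PEERS in weeks 0 to 16. These results are meant to inform a pivotal trial and a device submission.

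**Working it through.** **1. Plan's own figure.** The inputs are 48 completers and 15% non-completion (Sample Size Justification). 48 × 1.15 = 55.2, rounded up to 56, the stated number. Division gives 48 / 0.85 = 56.5, rounded up to 57. The stated 56 is therefore reproduced to within one person. Per arm this is 56 / 3 = 18.7 recruited, or 16 completers.

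**2. Sound content by label** (Treatment Interventions).
- Assessments: Sound Sweeps, Beep Seeker, Fine Tuning and In the Know, so 4 of 10.
- Exercises: Say What?, Voice Choice, In the Know and Auditory Ace, so 4 of 13.

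**3. Who is counted in item 4.** The table takes 16 per arm and assumes that everyone in Arm B attends PEERS at least once; Arm B app users who attend none would also drop out.

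| Reading | Source | Counted | Arm A left out |
|---|---|---|---|
| All allocated to CICADAS | SAP populations, opening summary | 32 | none |
| Given both, with Arm A joining at its first PEERS session | SAP definitions i and iv; Protocol, Treatment Arms | 16 to 32 | those gone before PEERS |
| Given both together (Arm B only) | SAP definition iv, read narrowly | 16 | all |
| Arm A never gets PEERS | SAP, Statistical Plan, which puts all three arms in a no-contact period after week 16 | 16 | all |

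In the last two rows, all of Arm A means 16 to 18.7 people. In the second row, an Arm A participant who drops the app but later attends PEERS is counted; one who leaves before any PEERS session is not.

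**4. Scale for the second row.** Expected all-cause Arm A non-completers = arm size × attrition, assuming equal attrition across arms:
- 15%: 16 × 0.15 = 2.4; 18.7 × 0.15 = 2.8.
- 30%: 16 × 0.30 = 4.8; 18.7 × 0.30 = 5.6.

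These figures cover the whole study and every cause. Some of these people may leave after starting PEERS, and an unknown share would leave because of the sounds.

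**5. Illustration (assumed).** Three of 16 in Arm A withdraw over the sounds before PEERS, each recorded as a side effect. None do in Arm B, and the other 13 in Arm A reach PEERS.
- Item 4, Arm B only: 0 of 16.
- Item 4, Arm B plus Arm A reaching PEERS: 0 of 16 + 13 = 29.
- All allocated to CICADAS: 3 / 32 = 9.4%.
- Arm A by itself: 3 / 16 = 18.8%.

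**6. Precision of a per-arm row.** The exact 95% upper limit for 0 of 16 is 1 − 0.025^(1/16) = 20.6%.

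**7. Timing.** The Adverse Effects form is scheduled only at V1, V3 and V4, and the SAP directs assessment efforts to participants with at least one hour on the app. For someone who stops within the first hour, the reason has to come from proctored first use, the coordinator's contacts or the exit interview.

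**The case against.** The strongest reply is that the reasons are obtainable and the design already responds to the pilot. Training is personalised. Focus groups, a two-week app trial and user interviews come before randomisation. First use is proctored, usability ratings are a primary outcome in the Protocol, and an exit survey covers enjoyment and usability. The pilot evidence is several people, without a denominator, from separate auditory and visual modules. Sensory over-reactivity is part of ASD, so the general line on worsening symptoms arguably covers it.

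Much of this stands. A reader might infer that the trial could not learn why people stop. The documents do not support that: the information can be gathered, and what is missing is a planned report of it. A reader might also infer that participants are not warned. The consent pages and form contents are not in the reviewed text, so only the Protocol's list can be judged. SAP item 3 is not visible either; the numbering runs 1, 2, 4, 5.

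Two further objections are right and shape the fix. A table beside item 4 would leave item 4's own population uncorrected. Reasons would come from the coordinator or PEERS clinician, whom the Blinding section lists as un-blinded, so a comparison of reasons by arm is open to ascertainment bias.

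The reply does not meet the population problem. None of these routes brings an Arm A participant who leaves before PEERS into item 4 under its formal definition.

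**Conclusion.** The point holds as a modest one. A known reason for stopping is absent from the itemised program-use risks and the anticipated withdrawal reasons, no SAP analysis reports stops by reason, and item 4 as formally defined omits Arm A participants who leave before PEERS. All of Arm A, about 16 to 19 people, is omitted if ITT-CU means Arm B only or if the SAP's no-contact text is followed.

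A reader might take 2.4 to 5.6 as a ceiling on those missed. It is not. The figures are expected counts under equal attrition, the pilot rate is given only as above 30%, and the stricter readings omit the whole arm. Nor does the gap between 38.5% and 73.2% completion measure aversion: the modules were separate, no denominators are given, and non-completion had other causes.

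For participants who are counted, item 4 could still read zero if such stops are not recorded as adverse effects. Whether that would happen cannot be told without the forms.

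**What to change.** 1. **SAP item 4.** Analyse it by arm among all randomised participants who started their assigned app, including Arm A whether or not they attended PEERS.
2. **SAP, beside item 4.** Report by arm the number and proportion who stopped the app or withdrew in weeks 0 to 16, by recorded reason, with auditory or sensory aversion as one category. Take the reason from the exit record or from the discussion already required before a participant stops the app.
3. **Protocol.** Add aversion to, or distress from, auditory or sensory stimuli to the program-use risks, worded identically for all arms, and name it in Withdrawal from the Protocol as an anticipated reason for stopping. Identical wording is accurate because "All participants, regardless of treatment group, will complete the ten sensory processing assessments before and after the first intervention period".

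**Cost.** A revised denominator, one descriptive table, one risk line and one sentence. No visit or staff is added, and the Study Exit form may already have a reason field.

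**Downsides.** Precision is low: 0 of 16 is compatible with up to 20.6%. Naming the effect may prime complaints, and it gives a slight allocation cue because the control app is matched as visual. Since un-blinded staff record the reasons, the comparison by arm should be labelled descriptive only.

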## Data Management

Data collected in this study may include paper forms for consent/assent forms and some assessments from clinician- or psychometrician-administered structured interviews, neuropsychological or functional assessments. Other assessments will be administered remotely and collected electronically through REDCap servers or the program platform hosted on Posit Science servers. Fully executed consent/assent forms completed site study personnel and securely stored at the site. With the exception of dates that assessments are completed, personally identifying information collected will not be stored with study assessment or performance data on the CICADAS and Active Control apps on Posit Science servers. Personally identifying information voluntarily disclosed by participants on the Zoom platform during the intervention will be accessible to the research team. Participants are informed that the research team will be monitoring their chat history on the Zoom platform. Prior to entering the participant's study record, direct identifiers (names, email addresses) will be redacted. De-identified, study-related data collected on paper and will be recorded into a secure, web-based electronic case report form (eCRF). This system meets all relevant privacy and security standards for electronic clinical trial data entry and storage, as well as the Health Insurance Portability and Accountability Act (HIPAA) standards for confidentiality and privacy.

Following consent, each participant will be assigned a standardized Participant Identification Number (PIDN) composed of digits to identify the study and 3 digits to identify the participant. The digits will begin with "001" for the first consented participant and ascend thereafter. All eCRF data entry will be de-identified, using the PIDN only and not the participant name, but will include the date of the assessment administration.

Participants may email site study personnel with questions or concerns, or to make arrangements for study visits. If deemed significant and relevant to the participant's study record, de-identified emails may be saved to the participant's study file. To de-identify emails, all direct identifiers (name, email address, date of birth, etc.) will be redacted from the email in PDF format. Site study personnel will place black bars over any directly identifying information. The redaction will be verified by a secondary staff member for accuracy and completion to ensure patient privacy prior to being uploaded for permanent storage. The dates of communication will be maintained in the emails to provide context for the conversation.

Site study personnel will transcribe and upload de-identified data and de-identified source documentation into the study database for the purpose of data monitoring. Periodic analysis of the data will be performed in order to examine the expected distributions of data, and to identify outliers for possible data mistakes. PSC data management personnel and site study personnel will interact frequently throughout the study to accomplish the quality goals of the data management process through the below process.

Periodic analysis of each data field (across all cases) will be performed in order to examine the expected distributions of data, and to identify outliers for possible data mistakes. Particular attention will be paid to the following:

- *Data Cleaning:* All eCRFs are automatically reviewed to check for omitted data and data inconsistencies. These deficiencies are required to be resolved at the point of data entry to prevent errors from entering the system.
- *Data Editing:* Each data record is evaluated on a regular interval. Any discovered error is then referred to the Investigator Designee within the Electronic Data Management (eCRF) System via the Data Monitor. The Investigator Designee will review the queries and make the corrections through the eCRF system. All such changes are automatically logged to allow a complete audit trail and recovery to any point in the change log if required.
- *Data Update:* The cycle of data editing will be ongoing until all the data are clean. If further data entry or source documentation errors are discovered during review, the corrections will be made at that time through the eCRF system.
- *Data Back-up:* The eCRF system employs an automatic continuous replication system to ensure that all data including change logs and access logs are replicated to two independent remote servers. At any point, the system is capable of emitting the entire store of eCRFs as paper CRFs for offsite storage or auditing if required.

We will take all standard and appropriate steps to protect the privacy and confidentiality of participants in this trial. At enrollment participants will be assigned a PIDN as described above, and all study data collection derived from that participant will be coded by PIDN. All

eCRF pages, including those with demographic as well as assessment data, will have the PIDN on them rather than the participants name. Dates that assessments are completed and date of birth will be collected. Personally identifying information voluntarily disclosed by participants on the Zoom platform during the intervention will be accessible to the research team. Prior to entering the participant's study record, direct identifiers (names, email addresses) will be redacted. Accurate and complete study records will be maintained and stored in a confidential manner so as to protect the confidentiality of participant information.

The eCRF system runs on remote servers not physically accessible to any study staff; all electronic access to the eCRF system is logged and regularly reviewed for any inappropriate access. All study related paper materials will be stored in locked file cabinets inside of locked rooms when not in use. During remote procedures, study personnel may shred the original paper documents after Posit Science has completed the data monitoring and reconciliation process and approved shredding of documents. Until documents are ready for shredding, they will be stored by the respective study personnel with limited access until the documents are shredded or transferred to the Study Site. All participant use of the CICADAS and Active Control programs will use a login based on the PIDN, and study programs will not collect or store any personally identifiable information on the laptop or on PSC servers, with the exception of dates that assessments are completed. Participants will choose whether to use their first name or an alias for the Zoom account.

We note this protocol does collect sensitive information, i.e. when assessing suicidal ideation, that may result in a reporting requirement to state or local authorities. The site is expected to follow standard institutional policies in such cases to ensure the protection of participants and proper reporting. If study personnel become aware of specific issues outside of the ordinary data collection procedures (e.g., child abuse) they will follow established institutional procedures already in place as appropriate for their local jurisdiction to report such knowledge.

